9.3 Populations for Analyses

The analysis population for each Specific Aim is below:

Specific Aim 1

- Key clinic personnel who complete the semi-structured in depth phone interview (6-8 staff per clinic)
- Clinic personnel who complete the online clinic personnel survey (all staff, up to 15 per clinic)
- Using administrative records, sites will report the total number of patients viewing the DA and the total number of patient visits during the active study time frame.

Specific Aim 2

- All enrolled participants who complete the baseline visit, as well as those who complete the three and six month follow-up questionnaires
- Clinic personnel who complete the online surveys

Specific Aim 3

- Key clinic personnel from Aim 1+ 2 patients per site who complete the post-study semi-structured in depth phone interview. (6-8 key clinic personnel + 2 patients per site)
-

The protocol population will be all participants who attend all study visits and complete the trial.

9.4 STATISTICAL ANALYSES

9.4.1 General Approach

IDEAL investigators [name], [name], and [name] will oversee all qualitative data management and analysis for IDEAL Data Coordinating Center (DCC). [name] and [name] will oversee all quantitative data management and analysis for IDEAL DCC. The DCC is housed within the UAB School of Health Professions.

Questionnaires have been developed and tested before being uploaded into Qualtrics. Data will be entered into the electronic database (Qualtrics) using iPads. The DCC will ensure that the data collected and analyzed for this study are of the highest quality possible, and will be accomplished in part by having thorough edit checks as close to collection in time as possible, and updated as needed to guarantee high quality data through quality control and quality assurance. Edit checks will be reviewed by the statisticians, program manager, as well as other team members on an ongoing basis to evaluate whether any checks need to be added or any existing checks need to be modified. All data will be entered into the IDEAL electronic Data Entry System (eDES; Birmingham, AL) directly using iPads for seamless data management and auditing across the IDEAL sites. All quantitative analyses will be conducted using SAS (Cary, NC) Version 9.4 or higher or R-routines for specialty programs as needed. All qualitative analyses will be conducted with NVivo 12, available through the UAB School of Medicine.

9.4.2 Analysis of the Primary Efficacy Endpoint(S)

Specific Aim 1:

Qualitative: Emergent theme analysis, within each clinic and based on the CFIR domains, will be initially conducted. These themes will be used to identify the preferred implementation strategies for use in a clinic. These within-case themes also will be used to compare and contrast between clinics to identify unique and common barriers to implementation.

Quantitative: Univariate statistics (means, standard deviations) will be used to describe each clinic's learning environment and readiness to implement change. Spearman correlations will be estimated to assess how different aspects of the clinic's learning environment and readiness to implement change may vary across clinics. Similarly, t-tests and one-way ANOVAs will be estimated to assess how the learning environment and readiness to change varies a

function of clinic characteristics (e.g., location, private vs. academic). Penetration will be assessed by evaluating the proportion of eligible patients reviewing the DA overall and in each site. Simple proportions and 95% confidence intervals will be computed. Patient healthcare utilization outcomes (e.g., inpatient visits and ER/urgent care visits) will be assessed similarly.

The results of the qualitative and quantitative analyses described above will be consolidated to construct a profile or “case study” for each clinic.

Specific Aim 2:

Targeted participants for this aim are (1) age \geq 18 years with a diagnosis of lupus from participating clinics. Objective measures will be assessed in both clinic personnel and in patients. Clinical personnel will evaluate perceived acceptability of intervention measure for the DA, perceived DA implementation success, and perceived DA permanence. All will be assessed on an ordinal scale (strongly disagree = 1) to (strongly agree = 5). Similarly, patients will evaluate perception of DA usefulness, patient satisfaction for the DA, perceived intervention appropriateness measure for the DA, and perceived feasibility of intervention measure for the DA. All of these patient assessments will be measured on a Likert-type scale.

For individual-level outcomes, initial analyses will focus on how clinic personnel and patient perceptions change over time. We will examine mean levels (total change) and patterns of change (growth trajectories) while controlling for differences between clinics using multivariable models that account for repeated measures and clinic clustering of patients (i.e., generalized estimating equations (GEE) with robust standard errors). The second component of our evaluation of **Aim 2** will use fuzzy set Qualitative Comparative Analysis (fsQCA) to assess the effectiveness of implementation strategies for clinic-level outcomes. fsQCA is a case-oriented approach that examines relationships between conditions (similar to explanatory variables in regression models) and outcomes using set theory to answer the question: “what conditions, alone or in combination, are necessary or sufficient to produce an outcome?”

For patient-physician communication analysis, question-asking, assertive responses, and expressions of concern will be coded as patient participation; supportive talk and partnership building by provider will be coded as active physician communication.

Specific Aim 3:

Similar to **Aim 1**, emergent theme analysis within each clinic will be initially conducted. These themes will focus identify the implementation lessons learned by the clinics, including and especially the implementation challenges faced by the clinic throughout the study, and their opinions of the opportunities and challenges to sustaining use of the DA once the study ends. These within-case themes also will be used to compare and contrast between clinics to identify common lessons learned and ideas for how to sustain the DA moving forward.

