8 STUDY ASSESSMENTS AND PROCEDURES

This study will be coordinated by the University of Alabama at Birmingham (UAB). All study visits and procedures will be performed at the United States, and at n = 16 sites. At least 35 participants are expected to be enrolled at each site. Enrollment will be competitive between sites.

Participants will be seen according to the details that follow:

Specific Aim 1: Clinic Personnel Survey/Semi Structured Interviews

This Specific Aim will: a) identify clinic staff and patient needs, and b) key contextual factors that inform targeted strategy selected influence implementation effectiveness, and sustainability. It will do so via two data collection efforts:

Clinic Personnel Survey

Up to 15 clinic personnel will be administered an online survey via Qualtrics® to assess their role in the clinic, clinic culture, and readiness to implement change. This will last between 20-25 minutes. Clinic personnel will be emailed a link to complete the survey. An automatic email will be generated in the Qualtrics® system and will go out to all non-responders every 24 hours for 5 days, or until the survey is completed.

Semi-Structured Interviews

Each site PI/ study coordinator will choose 6-8 key clinic staff that will be administered a 45-60 minute semi-structured interview either via phone or in person that will assess stakeholder needs and identify characteristics of the clinics (e.g., policy environment, physician, clinic, patient barriers) that influence DA adoption and choice of the implementation strategy. The interview protocol will be adapted to fit each time range and different key personnel. A link to the brief video animation introducing the decision-aid use and content along with the interview protocol and copy of the decision-aid will be emailed to clinic personnel prior to being interviewed. All interviews will be recorded and transcribed verbatim for accuracy.

Specific Aim 2: Implementation

Patient Baseline Visit

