9 STATISTICAL CONSIDERATIONS

9.1 STATISTICAL HYPOTHESES

Specific Aim 1: Targeted participants for this Specific Aim are key informants (interviews) and all clinic personnel (surveys). The purpose of this Specific Aim is to identify and quantify clinic and contextual characteristics (e.g., readiness for change, physician attitudes, patient barriers) to inform strategy component selection and influence implementation effectiveness of lupus DA to be evaluated in Specific Aim 2. As such the statistical approach for this component of Aim 1 is largely descriptive and there are no formal statistical null and alternative hypotheses. Specific descriptive statistics are described in the table below and further details are provided in Section 9.4. Penetration will be assessed by evaluating the proportion of eligible patients reviewing the DA overall and in each site. Overall rates and 95% confidence intervals will be computed. Patient healthcare utilization outcomes (e.g., inpatient visits and ER/urgent care visits) will be assessed similarly.

Specific Aim 1 Data Collection and Analyses		
Data Type	Data Collection Type	Analytic Methods
Quantitative	Online & paper survey, Organizational readiness for implementing change (ORIC); Team Learning & Psychological Safety Survey (TLPSS)/ Baseline	Individual & practice level summary statistics Correlation
Qualitative	Semi-structured interviews with key informants/ Baseline	Within-case/clinic thematic analysis of CFIR domains Cross-case/clinic comparison

Specific Aim 2: Targeted patient participants for this Specific Aim are (1) age \geq 18 years with a diagnosis of lupus from participating clinics; for individual-level outcomes, initial analyses will focus on how clinic personnel and patient perceptions change over time. The statistical null hypothesis is the assumption that there is no change over time versus

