9.2 Sample Size Determination

A power analysis for the quantitative portion of Specific Aim 2 was conducted using the following assumptions: (1) 16 clinics and (2) an intraclass correlation coefficient of 0.05. This provided us with a total confidence interval width of 5.3% for 10% of the total clinic population that is administered the lupus DA to a width of 8.1% , if 40% patients are administered the lupus DA. For outcomes on a 5-point Likert scale, the corresponding 95% CI widths for standard deviation of 0.5 and 2.0 on the mean score is estimated to be 0.09 vs. 0.35, respectively. For individual-level outcomes measured as a rate (e.g., # visits/1,000) or as means (e.g., Likert-scale), we anticipate small margins of error. A minimum number of proposed sites (n=16) are needed to comprehensively assess how different implementation strategies are influenced by and interact with different contextual conditions (different geographic areas, clinic type, and patient diversity) to affect implementation effectiveness, and thus, determine the generalizability of the study findings. However, given the proven effectiveness of the DA (original PCORI study), and in the spirit of dissemination and implementation research, we will continue to recruit to our proposed maximum sample size target of 3,000.

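### Section 9.4.2 points inpatient and ER/urgent-care visits to simple proportions while 9.2 expects a visit rate; the outcome is undefined, and no stated interval allows for clinic clustering or repeat visits

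*Combined protocol and SAP*

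**What the plan says.** Section 9.4.2, under Specific Aim 1, takes penetration (the share of eligible patients who review the decision aid) and states: "Simple proportions and 95% confidence intervals will be computed". The next sentence is the only analysis method given there for utilization: "Patient healthcare utilization outcomes (e.g., inpatient visits and ER/urgent care visits) will be assessed similarly".

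Section 9.1 has the same utilization sentence, but the sentence before it reads: "Overall rates and 95% confidence intervals will be computed".

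Section 9.2 puts visits on a different scale: "For individual-level outcomes measured as a rate (e.g., # visits/1,000) or as means (e.g., Likert-scale), we anticipate small margins of error".

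The notes to the schedule in section 2.2 say that utilization comes from administrative data. Section 9.3 lists what sites report from those records: a total of patients who viewed the decision aid and a total of patient visits over the active study period. It mentions no per-patient count of inpatient or ER visits and no observation time.

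**The concern.** A patient can be admitted, or attend urgent care, more than once. A visit rate and a proportion of patients with any visit are therefore different quantities and need different intervals. The analysis section points to the proportion and the sample-size section to the rate. Because the numerator, denominator and window are all open, the choice between them could be made after the data are seen.

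The interval is a problem whichever is chosen. A simple pooled interval treats all patients as independent, although they come from 16 clinics and section 9.2 itself assumes that patients within a clinic are correlated. For total visits there is the further problem that a binomial variance does not describe a recurrent count.

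Utilization is one of the few outcomes taken from records, and section 9.4.2 carries the Aim 1 results into each clinic's case-study profile. What is at stake is overstated precision and a figure whose meaning is unclear.

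**Working it through.** **Inputs.** Section 9.2 assumes ("1) 16 clinics and (2) an intraclass correlation coefficient of 0.05"). Section 8 gives the minimum clinic size: "At least 35 participants are expected to be enrolled at each site". Section 9.2 gives the maximum: "we will continue to recruit to our proposed maximum sample size target of 3,000". Clinics are taken as equal in size. The intraclass correlation is stated for the power analysis in general, so applying it to utilization is an assumption.

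**The plan's own precision figures.** Section 9.2 gives no width for visit rates. Its only widths for a proportion are 5.3% at 10% and 8.1% at 40%, with no sample size stated. With N = 16 × 35 = 560 and total width 2 × 1.96 × √(p(1−p)/n):

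- without clustering: 4.97% and 8.12%
- with intraclass correlation 0.05: 8.17% and 13.33%

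At N = 560 the 8.1% is matched only if clustering is ignored. The 5.3% is not matched by Wald, Wilson, exact or continuity-corrected intervals. That is a separate matter and does not decide this point, but section 9.2 cannot be relied on to show that clustering was already allowed for.

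**Reading 1: proportion of patients with any visit.** Design effect = 1 + (m − 1) × 0.05. The standard error is understated by the square root of the design effect.

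| Patients | m per clinic | Design effect | SE factor | Effective n |
|---|---|---|---|---|
| 560 | 35 | 1 + 34 × 0.05 = 2.7 | 1.64 | 207.4 |
| 3,000 | 187.5 | 1 + 186.5 × 0.05 = 10.325 | 3.21 | 290.6 |

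The factor grows with recruitment because the effective sample size cannot pass 16/0.05 = 320, while the simple interval goes on shrinking. At p = 10%, the simple width falls from 4.97% to 2.15%, and the clustered width only from 8.17% to 6.90%. Actual coverage of a nominal 95% interval is 2Φ(1.96/factor) − 1. This gives 2Φ(1.19) − 1, about 77%, at 560 patients and 2Φ(0.61) − 1, about 46%, at 3,000.

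**Reading 2: total visits put into a binomial interval.** The documents give no visit rate or dispersion, so the values below are assumed: mean μ visits per patient and negative-binomial variance μ + kμ², with k from 0 to 4. The ratio of binomial to correct width, before clustering, is √(μ(1−μ)/(μ + kμ²)) = √((1−μ)/(1+kμ)).

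| μ | Visits per 1,000 | Any visit (k = 4 to 0) | Width ratio (k = 4 to 0) | Coverage |
|---|---|---|---|---|
| 0.1 | 100 | 8.1–9.5% | 0.80–0.95 | 88–94% |
| 0.3 | 300 | 17.9–25.9% | 0.56–0.84 | 73–90% |
| 0.5 | 500 | 24.0–39.3% | 0.41–0.71 | 58–83% |

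At μ of 1 or more, p(1−p) is zero or negative and no binomial interval exists. Clustering would widen the correct interval further.

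**The case against.** **The wording is loose rather than contradictory.** A reader might infer that 9.4.2 and 9.2 contradict each other outright. The documents do not go that far. *Similarly* is imprecise, the 9.2 text is a parenthetical example that does not name inpatient or ER visits, and 9.1 speaks of rates. But the rates in 9.1 refer to the same penetration proportion, so 9.1 does not settle the matter.

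**A proportion is a valid outcome.** A reader might also infer that the estimate itself would be wrong. It would not be if the outcome is any visit, yes or no; repeat visits and overdispersion then do not matter. The estimate goes wrong only if visit totals enter a proportion or if observation time differs between patients. The clustering problem remains, for the pooled interval but not for single-clinic intervals.

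**Staggered enrolment.** Recruitment from Q2 to Q10 might suggest unequal follow-up. Sections 2.1 and 8 give each patient up to six months, so different start dates do not by themselves produce it. What stands is that no section ties utilization to those six months.

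**Clustered models are already planned.** Section 9.2 calls visit rates individual-level outcomes, and sections 9.1 and 9.4.2 plan GEE with clinic clustering for such outcomes. That text sits under Aim 2 and is directed at changes in perceptions. Utilization has its own method sentence under Aim 1.

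**The clinics could be treated as fixed.** An interval describing only these 16 clinics would not need the clustering inflation. Section 9.2, however, assumes an intraclass correlation and appeals to generalizability.

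**Aim 1 is descriptive.** This is correct: there are no formal hypotheses, and no test decision is at risk.

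**Conclusion.** The point holds as an undefined outcome with an unsuitable pooled interval. If the outcome is any visit, the simple pooled standard error is too small by a factor of about 1.64 at 35 patients per clinic and about 3.2 at 3,000 patients. This assumes that the plan's intraclass correlation of 0.05 applies to utilization and that clinics are of equal size. If total visits are used, a binomial interval is also invalid. Its error is small at about 100 visits per 1,000 and large at 500 per 1,000, but these rates are assumed, and the documents cannot fix the size. They do not support saying that the estimate is necessarily wrong, that follow-up is necessarily unequal, or that one multiplier describes the effect of repeat visits. The consequence is misreported precision for a descriptive outcome. It should be corrected before analysis.

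**What to change.** In section 9.4.2, replace the utilization sentence with text to this effect:

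> Inpatient visits and ER/urgent-care visits are counted per patient from baseline to 6 months. Visits per patient-time are estimated by Poisson or negative-binomial GEE with log follow-up time as offset and robust standard errors clustered on clinic. The proportion of patients with at least one visit is reported with a clinic-clustered interval.

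With only 16 clinics, the robust errors should carry a small-sample correction. The window should close on a fixed day rather than at the follow-up contact, because section 10.5 allows the 6-month contact anywhere from 151 to 356 days. Sections 9.1 and 9.2 should then name the same quantities and state the unit of the 1,000, and 9.3 should list the data needed.

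The cost is wider intervals and a change to the data request. Section 9.3 mentions only site totals, so sites would have to be asked for per-patient visit counts and observation time; nothing in the documents shows that these are already supplied. If only totals can be obtained, report clinic-level rates with an interval based on the variation between the 16 clinics.

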9.4.3 Analysis of Secondary and Safety Endpoint(S)

The statistical analysis plan will be modified to incorporate analysis of any safety outcomes or secondary endpoints identified after initiation of the study as needed. An unintended consequence of the implementation of the lupus DA will be captured and measured accordingly.

9.4.4 Baseline Descriptive Statistics

Clinical characteristics and patient demographics will be collected. Descriptive statistics will be reported using means and standard deviations (or medians and quartiles) for continuous-type data and using counts and proportions for categorical-type data. For any by-group comparisons, the two-sample t-test (or Wilcoxon Rank Sum test, as appropriate)

will be used to evaluate continuous-type data. The chi-square test of independence (or Fisher's exact test, as appropriate) will be used to evaluate categorical-type data. Statistical significance will be evaluated at a 0.05 level. Descriptive statistics will be presented overall and by groups defined by implementation strategy.

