Sites will also have the option to choose from recommended Tailored Implementation Activities. These strategies are clinic-targeted and patient-targeted activities designed to stimulate participant recruitment and retention. Sites will choose either activity that is most relevant for implementation of the DA at their clinic and we anticipate that some sites will choose both activities. At the end of the study, all sites will be reviewed to determine with strategies were used throughout the duration of the study.

Clinic-targeted Activities:

- DA reminder in patient intake process
- Audit and feedback
- Team huddles/clinic meetings

Patient-targeted Activities

- Pre-visit web-based portal messages with
 - Access to decision aid via a link
 - Information regarding the study time demand
- Pre-visit delivery of paper-based version of decision aid
- Clinic poster about decision aid
- Decision-aid information through the waiting room TV/online kiosk

The DA will be given to all patient participants that meet the eligibility criteria during their regularly scheduled lupus clinic visit. Before reviewing the decision-aid, patients will view a short educational video on the purpose and use of the decision-aid. Questionnaires and the DA will be administered on an iPad, and questionnaires will take no more than 30 minutes on average, to keep responder burden low. Three and six-month follow-up questionnaires will be administered via phone, mail, or at the regularly scheduled clinic visit per the patient participant preference, and will last no more than 15 minutes.

In the event clinic personnel transition to a different position or leave the organization, they will be given a Clinic Personnel Exit interview* to assess the reason for departure, their view on the dissemination of the decision-aid into normal clinic flow, and the sustainability for future use.

Aim 2 Clinic Personnel Survey

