the alternative that there is a change over time. For the analytic approach we will examine mean levels (total change) and quantify with means (or proportions, as appropriate) and 95% confidence intervals. We will also examine patterns of change (growth trajectories) while controlling for differences between clinics using multivariable models that account for repeated measures and clinic clustering of patients (i.e., generalized estimating equations (GEE) with robust standard errors). Additional analyses may examine by-group comparisons of clinics determined by clinical characteristics (e.g., geographic areas, clinic type, and patient diversity) observed in Specific Aim 1. Any such by-group analyses will be conducted separately. A primary independent variable of interest is the type of strategy used for implementation. Following completion of the study, each sites strategies will be evaluated and sites will be grouped accordingly. A covariate allowing for testing group differences will be included in the multivariable models to assess whether trajectories differ by implementation strategy.

The second component of our evaluation of Specific Aim 2 will use fuzzy set Qualitative Comparative Analysis (fsQCA) to assess effectiveness of implementation strategies for clinic-level outcomes. fsQCA is a case-oriented approach that examines relationships between conditions (similar to explanatory variables in regression models) and outcomes using set theory to answer the question: “what conditions, alone or in combination, are necessary or sufficient to produce an outcome?” For patient-physician communication analysis, question-asking, assertive responses, and expressions of concern, will be coded as patient participation; supportive talk and partnership building by provider will be coded as active physician communication. Further details are provided in Section 9.4.

Specific Aim 3: Targeted participants for this Specific Aim are the same key clinic informants from Specific Aim 1 and 2 patients per clinic from Specific Aim 2. Similar to Specific Aim 1, the analytic approach is largely descriptive and there are no formal statistical null and alternative hypotheses. Specific descriptive statistics are described in the table below. Further details are provided in Section 9.4.

Specific Aim 3 Data Collection and Analyses		
Data Type	Interview Content	Analytic Methods

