9.4.7 Missing Data and Outliers

The rate of missing values will be evaluated on a variable-by-variable basis. Clinics and/or patients with extensive missing values will be deleted from all analyses. A clinic or patient with a missing value for any variable involved in a specific analysis will be excluded from that analysis only (case wise deletion). There are no plans for imputation of missing values. Theoretical assumptions for all statistical procedures will be evaluated (e.g., evaluation of normality, residual plots, and outlier evaluations). Any outliers will be inspected for data coding and entry errors and they will be corrected whenever appropriate. In the case of true outliers, sensitivity analyses with the specific values removed will be conducted in order to evaluate the robustness of the observed results.

In the event that there is insufficient (or excessive) variation in implementation strategies to create 2 clearly differentiable study groups, alternative definitions of the primary independent variable may be created (e.g., groups determined by number of strategies used or groups determined by percentage of staff trained).

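### The baseline tests in 9.4.4 ignore clinic clustering, so patient-level p-values between strategy groups would not hold the stated 0.05 level

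*Combined protocol and SAP*

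**What the plan says.** Section 9.4.4 opens with its scope: "Clinical characteristics and patient demographics will be collected". It then gives one general testing rule, beginning "For any by-group comparisons, the two-sample t-test (or Wilcoxon Rank Sum test, as appropriate" and continuing with chi-square or Fisher's exact test for categorical data. The threshold follows: "Statistical significance will be evaluated at a 0.05 level". The section closes with "Descriptive statistics will be presented overall and by groups defined by implementation strategy". No other grouping is named there, and clustering by clinic is not mentioned.

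Other sections show what a strategy group is. Under the tailored activities in 6.1, the choice is made by the site: "Sites will choose either activity that is most relevant for implementation of the DA at their clinic". Section 9.1 adds "Following completion of the study, each sites strategies will be evaluated and sites will be grouped accordingly". Section 9.4.7 shows that two groups are intended, since it provides for the case where there is not the right amount of variation "to create 2 clearly differentiable study groups".

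The plan does allow for clustering elsewhere. Section 9.2 assumes an ICC of 0.05 over 16 clinics, and 9.1 and 9.4.2 specify, for Aim 2 perceptions over time, "multivariable models that account for repeated measures and clinic clustering of patients".

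**The concern.** Strategy is constant within a clinic, so a comparison of strategy groups has at most 16 independent units, however many patients are enrolled. The tests named in 9.4.4 take every observation as independent. If they are run on patient-level characteristics that are even slightly correlated within clinics, the standard error is too small and the null hypothesis is rejected too often.

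The by-strategy baseline table is where a reader will judge whether self-selected strategy groups served similar patients. A p-value labelled as a 5% test would then flag differences in patient mix more often than 5% of the time when there is no systematic difference between strategies.

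**Working it through.** **Inputs from the plan.** 16 clinics and ICC 0.05 (9.2, for Aim 2 planning); at least 35 patients per clinic (section 8); a ceiling of 3,000 patients (9.2), or 3,000/16 = 187.5 per clinic if clinics are equal; level 0.05 (9.4.4); two groups (9.4.7).

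**Assumptions.** The tests are two-sided. No ICC is given for baseline variables, so 0, 0.005, 0.01 and 0.05 are used. The plan gives no split of clinics between groups, so 8:8, 4:12 and 2:14 were tried.

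**Step 1: formula.** With m patients in each clinic, the design effect is DE = 1 + (m − 1) × ICC, and the true size of a nominal 5% patient-level test is 2 × (1 − Φ(1.96/√DE)).

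| ICC | DE, m = 35 | Size, m = 35 | DE, m = 187.5 | Size, m = 187.5 |
|---|---|---|---|---|
| 0 | 1.00 | 5.0% | 1.00 | 5.0% |
| 0.005 | 1.17 | 7.0% | 1.93 | 15.9% |
| 0.01 | 1.34 | 9.0% | 2.87 | 24.7% |
| 0.05 | 2.70 | 23.3% | 10.33 | 54.2% |

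For example, at m = 35 and ICC 0.05: DE = 1 + 34 × 0.05 = 2.70, 1.96/√2.70 = 1.19, size 23.3%. The plan's 5% is reproduced at ICC 0 only, so the excess comes entirely from clustering.

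**Step 2: simulation of each named test.** 16 clinics of 35 patients, over the three splits; 20,000 runs (6,000 for Fisher). Continuous data used a normal clinic effect; binary data were beta-binomial with prevalence 0.1 and 0.4.

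| Test | ICC 0.005 | ICC 0.01 | ICC 0.05 |
|---|---|---|---|
| t | 6.8-7.0% | 8.5-9.4% | 23.1-24.0% |
| Wilcoxon | 6.7-6.9% | 8.4-9.0% | 22.5-23.3% |
| Chi-square | 6.8-7.4% | 8.6-9.4% | 21.7-23.9% |
| Fisher's exact | 5.1-6.6% | 6.9-8.2% | 20.4-23.5% |

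Fisher's test is lower because it is conservative to begin with: at ICC 0 it rejected in 3.6-4.7% of runs. A t-test on the 16 clinic means stayed at 4.7-5.3% across all ICCs and splits.

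**Step 3: precision when the clinic is the unit.** For 8 versus 8 clinics of 35, the 95% CI half-width for a mean difference, in SD units, is t(14) × √[(ICC + (1 − ICC)/35) × 2/8], with t(14) = 2.145. This gives 0.196, 0.210 and 0.298 at ICC 0.005, 0.01 and 0.05. Ignoring clustering, it is 1.96 × √(2/280) = 0.166.

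**The case against.** **Strategy groups are only presented, not tested.** The closing sentence of 9.4.4 does promise only presentation, and 9.1 uses by-group language for comparisons of clinics. But the testing rule covers every by-group comparison, the section includes patient demographics, and strategy is its only named grouping. The patient-level use is therefore within the rule, though not the only possible one. Characteristics with a single value per clinic are not affected.

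**The clinics are fixed.** In an observational case study of 16 named sites, one could ask only whether the patients of these clinics differ, and then between-clinic variance is not sampling error. The plan does not take that view: it assumes an ICC and models clinic clustering. The sizes above rest on the same random-clinic target.

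**The inputs are assumed.** This stands. The 0.05 is borrowed from Aim 2 planning, and at the two smaller ICCs with 35 patients per clinic the size is 7-9% against 5%. The two-group case is also assumed: 6.1 expects some sites to choose both kinds of activity, 6.3 expects 16 different approaches, and 9.4.7 allows other group definitions. The sizes cover two groups only.

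**Nothing important depends on it.** This also stands. No hypothesis or endpoint uses these p-values, which is why the point is minor.

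**Conclusion.** As written, the rule in 9.4.4 gives p-values with the wrong error rate when it is applied to patient-level baseline data between strategy groups. No other section repairs this, because the clustered models are specified for Aim 2 perceptions over time. With two groups, 35 patients per clinic and clinics as random units, the size of the t, Wilcoxon and chi-square tests is about 7%, 9% and 23% at ICC 0.005, 0.01 and 0.05. Fisher's test is at about 5-6%, 7-8% and 20-24%. Severity is low.

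A reader might infer more than the documents support:

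- **That the Aim 2 strategy comparison is compromised.** It is not; 9.1 and 9.4.2 place it in GEE models that account for clinic clustering.
- **That differences in patient mix between strategy groups are spurious.** The observed differences remain valid descriptions and possible confounders; only their p-values are in doubt.
- **That all four tests share the same inflation.** Fisher's test at ICC 0.005 is close to nominal.
- **That 16%, 25% and 54% are the expected sizes.** These are formula values for t-type tests if the 3,000 ceiling were reached with equal clinics. They show that inflation grows with clinic size; they do not forecast it.

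**What to change.** Add one sentence to 9.4.4:

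> Differences in patient characteristics between groups defined at clinic level, such as implementation strategy, will be reported descriptively without p-values, or, if tested, will use the clinic mean or proportion as the observation (up to 16 values) or a cluster-adjusted model with a small-sample correction.

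This needs no new data. Reporting without p-values costs no precision. If the differences are tested, fewer will reach 0.05: for 8 versus 8 clinics of 35, the half-width is 0.20 to 0.30 SD over the assumed ICCs, instead of the 0.17 SD obtained by ignoring clustering.
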